### 3.0 Introduction

This Statistical Analysis Plan (SAP) describes the statistical methods that will be used during the analysis and reporting of data collected under F. Hoffmann-La Roche Ltd Protocol WP40607.

This SAP should be read in conjunction with the study protocol and electronic case report form (eCRF). This version of the plan has been developed using the protocol dated 22-Oct-2018 (including all amendments up to this protocol date) and the final eCRF(s) dated 08-Jan-2019.

An approved and signed SAP is a requirement for database lock.

This SAP only covers the results that will be processed by the PRA Early Development Services (EDS) Biostatistics Department.

PRA EDS will perform the pharmacokinetic (PK) and safety and tolerability evaluation.

This SAP supersedes the statistical considerations identified in the protocol; where considerations are substantially different, they will be so identified. Any post-hoc or unplanned analyses, or significant changes from the planned analysis in this SAP performed to provide results for inclusion in the clinical study report (CSR) but not included in this SAP, will be clearly identified in [Section 9.8.2](#) of the CSR. Changes to planned analyses do not require an updated SAP but should be included in the CSR if significant.

### 4.0 Changes from Previous Version of Approved SAP

This is the first version of the SAP.

### 5.0 Study Objectives

This study will evaluate the PK of balovaptan.

#### 5.1 Primary Objective

- To determine the absolute oral bioavailability of a single dose of 10 mg balovaptan.

##### 5.1.1 Primary Endpoints

- Absolute bioavailability (F) for balovaptan at the indicated dose level.

#### 5.2 Secondary Objectives

- To determine the absolute oral bioavailability of a single dose of 50 mg balovaptan.
- To determine the absolute oral bioavailability of balovaptan after once daily doses of 10 mg or 50 mg for 14 days.
- To characterize the dose- and time-dependency of the PK of oral balovaptan.
- To determine plasma concentrations of [C]-labeled balovaptan, balovaptan, and its metabolites M2, and M3, following a single oral dose of balovaptan 10 mg or 50 mg together with a slow intravenous (IV) infusion of a microdose of [C]-labeled balovaptan.
- To determine plasma concentrations of [C]-labeled balovaptan, balovaptan, and its metabolites M2, and M3, following once daily oral dosing of 10 mg or 50 mg once daily (QD) for 14 days together with a slow IV infusion of a microdose of [C]-labeled balovaptan after the last oral dose.
- To evaluate the safety and tolerability of balovaptan 10 mg QD and 50 mg QD.

##### 5.2.1 Secondary Endpoints

- Absolute bioavailability (F) for balovaptan at the indicated dose level.

- Plasma concentrations and associated PK parameters for [C]-labeled balovaptan, balovaptan, and its metabolites M2, and M3, including but not limited to  $C_{max}$ ,  $t_{max}$ ,  $t_{1/2}$ ,  $AUC_{last}$ ,  $AUC_{inf}$ ,  $AUC_{0-24}$ ,  $C_{last}$ ,  $t_{last}$ ,  $\lambda_z$ , and (for [C]-parent only) CL on Day 1 and Day 14 and  $V_{ss}$  on Day 1 and Day 14.  
Any other parameter as appropriate (see Table 1)
- Adverse events (AEs), clinical laboratory values, vital signs, electrocardiogram (ECG), and physical examination.

### 5.3 Tertiary/Exploratory Objectives

- To determine whether genes relating to drug-metabolizing enzymes and/or drug transporter enzymes affect the PK and/or the safety profile of balovaptan.

- [REDACTED]

#### 5.3.1 Tertiary/Exploratory Endpoints

- The pharmacogenetics of metabolizing enzymes, transferases, transporters, etc., possibly involved in the absorption, distribution, metabolism and excretion of balovaptan and its major metabolites (e.g., CYP3A and P-glycoprotein). The results for pharmacogenetics may be pooled with data from other studies of balovaptan and will be reported separately.

- [REDACTED]

## 6.0 Study Design

This study is a non-randomized, open-label, parallel group, two-treatment study in healthy volunteers to investigate the absolute oral bioavailability of balovaptan. The study is conducted at 1 site in the Netherlands.

Two cohorts of 8 subjects each are included in the study. Cohort 1 receives 10 mg balovaptan and Cohort 2 receives 50 mg according to the following regimen:

#### Period 1:

- Day 1: a single oral dose of 10 or 50 mg balovaptan after at least 10 hours of fasting, followed 1.25 hours later by a 15-minute IV infusion of [C]-labeled balovaptan 0.1 mg.

#### Period 2:

[figure not shown]
- Day 1 to Day 14: oral doses of 10 or 50 mg balovaptan QD; on Day 7 and Day 14 study drug administration will take place after at least 10 hours of fasting.
- Day 14: the final oral dosing will be followed 1.25 hours later by a 15-minute IV infusion of [C]-labeled balovaptan 0.1 mg.

[REDACTED]

The target population will be healthy male (at least 4 male subjects enrolled per cohort) and female subjects, aged 18 to 65 years, inclusive, at screening. At least 4 subjects enrolled per cohort should be aged 18 to 50 years, inclusive, at screening.

Figure 1 presents an overview of the study design.

**Figure 1: Study Schema**

IV = intravenous; QD = once daily

a Day 14 of Period 1 is Day -1 of Period 2

## 6.1 Sample Size Considerations

This is an exploratory study for which no formal statistical hypothesis will be tested, and therefore the sample size is chosen to estimate the absolute bioavailability of the 10 mg single dose with sufficient precision. A total of 8 subjects per cohort are to be enrolled with the target of at least 6 subjects available for the primary PK analysis (i.e., having taken a single dose of 10 mg on Day 1 and completed all PK assessment up to Day 10). If the number of subjects providing PK data from the multiple dose parts of the study is lower than 6 for either cohort more subjects may be enrolled.

Assuming a within-subject variability of around 35% it can be estimated that with 6 subjects the half-width of the 90% confidence interval (CI) for the ratio of geometric means of the microdose IV kinetics with that from the oral dose (i.e. CL versus CL/F) would be obtained by dividing/multiplying the ratio estimate by a factor of 1.50. The within-subject variability value of around 35% has been identified as a reasonable assumption: it is smaller than the observed 42% between-subject variability for the apparent clearance of distribution (CL/F) from a single oral 10 mg dose in study WP40038, and it considers that the reference will be obtained from IV kinetics, which is expected to be less variable than oral kinetics.

## 6.2 Randomization

Not applicable, this is a non-randomized study.

## 7.0 Overview of Planned Analysis

### 7.1 Changes from Protocol

There are no changes from the protocol.

### 7.2 Interim Analysis and Key Results

No interim reporting is planned for this study.

---

## 7.3 Final Analysis

Draft Tables, Figures and Listings (TFLs) will be provided with the draft CSR. After Sponsor comments have been incorporated, the TFLs will be finalized and incorporated in the final CSR.

## 8.0 Data Review

### 8.1 Data Management

Data handling, transfer and coding will take place under the PRA Data Management Plan for the study.

### 8.2 Acceptance of Data for Summarization

Programming of analysis datasets and TFLs may be ongoing during the data management of the study. However, programming of analysis datasets and TFLs will be completed and quality controlled (QC'd) after database lock. Only quality assured (QA'd) results released by the Safety Laboratory, Bioanalytical Laboratory, or other external data source will be used for the programming of analysis datasets and TFLs for the final report. Any data values requiring investigation or corrections that are identified while programming the analysis datasets and TFLs will be sent to the project Data Manager. If the issue affects the TFLs the Programmer or Statistician who identified the issue will follow it to resolution.

## 9.0 Definitions and General Analysis Methods

### 9.1 Analysis Data Presentation

#### 9.1.1 Rounding

In listings, all data (except the PK data) will be presented with the same precision as the original data. Derived data will be rounded for presentation purposes.

For descriptive statistics of safety data, range values will be presented with the same precision (number of decimals or significant digits) as the data they are calculated from, median, arithmetic mean values with 1 more decimal digit, standard deviation (SD) with 2 more decimal digits. Percentages will be rounded to integers.

For the rounding of derived PK parameters Appendix 2 of the Roche Clinical Pharmacology Guideline will be followed [3]. For all PK parameters except  $t_{max}$ ,  $t_{last}$  and  $t_{1/2}$ ; individual subject data, range values, median, arithmetic mean, geometric mean and SD will be presented with a precision of 3 significant digits. The coefficients of variation (CV) with 1 decimal digit.

All individual data and descriptive statistics for  $t_{max}$ ,  $t_{last}$  and  $t_{1/2}$  will be reported with 2 decimals, except for the CVs, which will be presented with 1 decimal digit.

#### 9.1.2 Imputation

Except for the substitution of any PK concentrations below the lower limit of quantification (LLOQ) (see [Section 16.2](#)) and missing start or end date/times of AEs for the calculation of onset and duration (see [Section 17.1.1](#)), any missing data will not be imputed.

### 9.1.3 Descriptive Statistics

Unless otherwise indicated, continuous variables will be summarized with the following descriptive statistics:

- n (number of observations),
- nmiss (number of missing observations),
- (arithmetic) mean,
- SD,
- minimum (min) value,
- median, and
- maximum (max) value.

Categorical data will be summarized with frequencies and percentages. Percentages by categories will be based on the number of subjects exposed within a treatment.

For categorical data the categories will be presented in the tables exactly as they appear in the CRF / Database.

### 9.1.4 Pooling

Summary statistics will be calculated by treatment (and time point, if applicable).

### 9.1.5 Unscheduled Measurements

Unscheduled measurements will be included in the listings. Except for unscheduled measurements used for baseline, unscheduled measurements will be excluded from the descriptive statistics and statistical analysis.

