4.5.5.1 Laboratory Samples

Laboratory samples will be collected at the time points indicated in [Appendix 1](#). Additional blood or urine samples may be taken at the discretion of the Investigator if the results of any test fall outside the reference ranges, or clinical symptoms necessitate additional testing to monitor subject safety.

Samples for the following laboratory tests will be sent to the study site's local laboratory for analysis:

- **Hematology:** leukocytes, erythrocytes, hemoglobin, hematocrit, platelets, absolute and percent differential WBC count (neutrophils, eosinophils, basophils, monocytes, lymphocytes).
- **Coagulation:** prothrombin time (International Normalized Ratio [INR]) and activated thromboplastin time (aPTT).
- **Blood chemistry panel:** sodium, potassium, chloride, bicarbonate, glucose (fasting), urea, creatinine, total protein, albumin, phosphate, calcium, total and conjugated bilirubin, alkaline phosphatase, alanine aminotransferase (ALT), aspartate aminotransferase (AST), gamma-glutamyl transferase (GGT), CPK, lactate dehydrogenase (LDH).
- **Urinalysis:** A midstream, clean-catch urine specimen will be collected for dipstick analysis of pH, glucose, leukocytes, nitrites, protein and blood. Microscopy will be performed if abnormalities are observed and if deemed necessary by the Investigator or designee, in particular when blood or protein is positive or strong positive. If there is an explanation for the positive dipstick result, it should be recorded, and there is no need to perform laboratory for microscopy and culture.
- **Drugs of abuse** (including cannabinoids, amphetamines [including ecstasy], methamphetamines, opiates, methadone, cocaine, benzodiazepines, and barbiturates), alcohol and cotinine will be measured in urine at screening and each admission to the CRU (Day -1 and Day 14).
- **Viral serology:** HIV-1 and HIV-2 antibodies, HBsAg, HepBc-antibody and HCV antibody at screening only.
- **Pregnancy test:** follicle-stimulating hormone (FSH) and beta-human chorionic gonadotropin (serum pregnancy test) will be performed at screening in all females. At other time points, a serum pregnancy test will be performed in all females.

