### 17.1.3 Laboratory Data

Clinical laboratory data will be presented using units from the study data tabulation model (SDTM) Controlled Terminology.

All laboratory data will be listed, including laboratory variables not listed in the protocol. A separate listing, including out-of-range values will also be provided. Normal ranges will be used directly from the clinical laboratory.

Descriptive statistics summarizing continuous laboratory results of clinical chemistry, hematology and urinalysis (observed and derived changes from baseline) by treatment and scheduled time will be provided.

Additionally, for CPK (chemistry) a frequency table for the following ranges will be added:

- $\leq 2$  times upper limit of normal (ULN)
- $> 2$  and  $\leq 5$  times ULN
- $> 5$  and  $\leq 10$  times ULN
- $\geq 10$  times ULN

For categorical urinalysis parameters frequency tables, showing the number of subjects in a category (n) and the percentage of the total number of subjects per treatment (N), will be provided. Sporadic urinalysis tests that were performed when abnormalities were observed (i.e. microscopy/sediment) will only be listed.

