### 17.1.5 Electrocardiograms

All ECG parameters (including changes from baseline) and the corresponding abnormalities and physician's conclusions will be listed by subject.

The observed measurements for all ECG parameters (including T-wave, U-wave) and the corresponding abnormalities will be listed for all time points. The means of triplicate measurements for continuous parameters and the change from baseline of the mean triplicate measurements at each scheduled time point will be listed by subject.

Descriptive statistics will be provided to summarize mean continuous ECG parameters (observed and changes from baseline) by treatment and scheduled time. A frequency table will be provided as well to summarize the ECG parameters by physicians conclusion (normal, abnormal not clinically significant, abnormal clinically significant). Additionally a frequency table for the following pre-specified QTcF ranges (for the rounded values) will be added:

ECG Parameter	Raw Value	(Positive) Change from Baseline
QTcF (msec)	$\leq 450$ , $> 450$ and $\leq 480$ , $> 480$ and $\leq 500$ , $> 500$	$\leq 20$ $> 20$ and $\leq 30$ , $> 30$ and $\leq 60$ , $> 60$

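### The CPK and QTcF band tables leave out post-baseline unscheduled values, so they can show a subject in a lower category than the worst one reached

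*SAP*

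**What the plan says.** SAP 9.1.5 sets one rule for all data types. "Unscheduled measurements will be included in the listings", but with a single carve-out ("Except for unscheduled measurements used for baseline") "unscheduled measurements will be excluded from the descriptive statistics and statistical analysis".

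SAP 9.1.3, whose title is Descriptive Statistics, covers category counts as well as means: "Categorical data will be summarized with frequencies and percentages". Percentages there are based on the subjects exposed within a treatment.

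Two safety tables are built on thresholds:

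- SAP 17.1.3: "Additionally, for CPK (chemistry) a frequency table for the following ranges will be added". Four bands in multiples of ULN follow (Table 14.3.3.5).
- SAP 17.1.5: "Additionally a frequency table for the following pre-specified QTcF ranges (for the rounded values) will be added". Four bands for the raw value and four for the change from baseline follow (Table 14.3.4.4).

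Neither section says how unscheduled values are handled. Neither says which of a subject's several values decides the band.

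On extra testing, Protocol 4.5.5.1 provides: "Additional blood or urine samples may be taken at the discretion of the Investigator if the results of any test fall outside the reference ranges". The same sentence adds clinical symptoms as a second trigger.

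**The concern.** Excluding unscheduled values is sensible for means by time point, where an off-schedule value has no column to sit in. A threshold table answers a different question, namely how many subjects went above a given level. Leaving out part of a subject's post-dose data can lower that count.

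For CPK the omitted draws are not a random subset. The protocol links them to an out-of-range result or to symptoms, so they come from subjects in whom a high value is more likely. Safety and tolerability is a stated secondary objective, and with eight subjects per cohort one reclassified subject visibly changes a column. At stake is a summary table with nobody in a high band when a listing shows that someone reached it.

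**Working it through.** The plan states no figure on this point, so there is none to reproduce. The check is of the text, followed by simple arithmetic.

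**1. Does the rule reach the tables?** 9.1.5 removes unscheduled values from descriptive statistics. 9.1.3 places frequencies under that title. 17.1.3 and 17.1.5 ask for frequency tables and contain no override. Read as written, the rule applies to both.

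**2. Direction of the error.** For one subject in one treatment, let S be the highest scheduled post-dose value and U the highest unscheduled one. The table uses band(S); the worst band reached is band(max(S, U)).

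- Since max(S, U) ≥ S, the tabulated band is never too high.
- It is too low only when U lies in a higher band than S.
- Invented example: S = 6 and U = 12 times ULN is tabulated in the band above 5 and up to 10, but belongs in the top band. If the repeat is 4 times ULN, nothing changes.
- If there is no scheduled post-dose value, U is not counted at all.

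**3. How much is scheduled?** From the schedule footnotes (Protocol Appendix 1, SAP Appendix 2):

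| | After the Period 1 dose, before Period 2 dosing | During the 14 days of daily dosing | Afterwards |
|---|---|---|---|
| Chemistry (CPK) | Period 2 Day -1 | Day 11 predose | Day 18, follow-up |
| ECG | Period 1 Day 10, Period 2 Day -1 | Days 6 and 11 predose | Day 18, follow-up |

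Period 2 Day -1 is Period 1 Day 14, which is 14 − 1 = 13 days after the single dose. SAP 9.2.3 starts each analysis period one day before dosing, which appears to place this draw in Period 2. Treatments A and C (the single doses) would then have no scheduled post-dose CPK in their own analysis period. SAP 9.2.3 also ends Period 1 at that same point, so the assignment is not beyond doubt.

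**4. Are unscheduled values foreseen?** For blood and urine, yes (Protocol 4.5.5.1). For ECGs, the visible text has no equivalent provision, though much of the safety section is redacted.

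**5. Size.** With 8 subjects per cohort:

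- one subject misplaced: 1/8 = 12.5 percentage points
- two subjects misplaced: 2/8 = 25.0 percentage points

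The documents do not say how often a subject's worst value would be unscheduled and in a higher band. Suppose each subject has the same independent chance q (an assumption). The chance that at least one of 8 is misplaced is 1 − (1 − q)^8:

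| q | 1 − (1 − q)^8 |
|---|---|
| 2% | 15% |
| 5% | 34% |
| 10% | 57% |
| 20% | 83% |

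The spread shows only that the answer depends on q.

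**6. Band edges.** In 17.1.3 the third CPK band includes exactly 10 times ULN and so does the top band. A value of exactly 10 falls in both.

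**The case against.** There is a fair case for leaving the rule alone.

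- **The values are visible elsewhere.** They stay in the listings, and out-of-range laboratory values appear in Table 14.3.3.1, which sits with the CPK table among the end-of-text outputs. Protocol 5.3.5.5 requires a laboratory result with symptoms, or one judged clinically significant, to be reported as an AE. Protocol 5.2.1 covers symptomatic ECG deterioration in the same way. Such events reach the TEAE tables (SAP 17.1.1). This stands, and it confines the defect to the two band tables.
- **The value that triggers a repeat is kept.** When a scheduled result prompts the repeat, that result stays in the table, and the repeat may be lower or normal. A reader might infer that the dropped values are always the extreme ones, or that the tables are biased toward showing nothing. The documents do not support that; understatement is conditional, as in step 2.
- **Nothing visible provides for unscheduled ECGs.** This also stands. A reader might treat the two tables as equally affected, but the QTcF part applies only if such ECGs are taken.
- **The tables are not labelled as worst-value tables.** SAP 9.1.4 allows summaries by time point where applicable, and for by-time-point counts the exclusion is reasonable. This stands as a possible reading. It also shows that the counting rule is undefined and has to be written down in any case.
- **A maximum rises with the number of tests.** Extra testing is discretionary and the study is open-label. Protocol 3.3.1 accepts that knowing the treatment may affect tolerability reporting. Testing intensity could therefore differ between the 10 mg and 50 mg cohorts. This is a real cost of the fix, and the footnote proposed below is there to expose it.

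None of these points makes the band tables correct as summaries of how high values went.

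**Conclusion.** The point holds within limits. As written, SAP 9.1.5 keeps post-baseline unscheduled values out of Table 14.3.3.5, and out of Table 14.3.4.4 if unscheduled ECGs exist. Either table can then understate a subject's worst category and cannot overstate it. Each affected subject is 12.5 percentage points of a column of 8. How many would be affected cannot be estimated from the documents.

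The CPK case is the stronger one, because extra samples are expressly allowed and scheduled on-treatment chemistry is thin. The conclusion rests on three readings: that 9.1.3 brings frequency tables under 9.1.5, that the band tables are meant to show how high each subject went, and, for the single-dose columns, that Period 2 Day -1 belongs to Period 2.

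A reader might infer that the SAP conceals or discards abnormal values. It does not, since they are listed and, where symptomatic or clinically significant, reported as AEs. The primary analysis of bioavailability is untouched. This is a cheap improvement to two summary tables.

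**What to change.** Keep 9.1.5 for summaries by time point. Add to 17.1.3 and 17.1.5 that Tables 14.3.3.5 and 14.3.4.4 classify each subject once per treatment by the worst post-dose value, scheduled or unscheduled, with a footnote marking subjects whose worst value was unscheduled. State in the same place which treatment the Period 2 Day -1 sample counts toward, since it follows the Period 1 dose but precedes Period 2 dosing. Change the top CPK band to >10 times ULN so that it no longer overlaps the band ending at 10.

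The cost is a short SAP edit and a small programming change, with no new data. The tables may look slightly less favourable. The worst value will depend partly on discretionary testing, which could differ between cohorts in an open-label study; the footnote lets a reader see where that happened.

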## 9.2 Analysis Data Definitions

### 9.2.1 Baseline Definition

Unless otherwise stated, baseline for post-dose evaluations within each period is defined as the last observation recorded before the first study drug administration in Period 1. The last observation can be an unscheduled / repeated measurement. Baseline for Electrocardiograms (ECGs) is derived as the mean of the triplicate pre-dose measurements of pre-dose assessments taken in Analysis Period 1.

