Appendix 1 Schedule of Activities (cont.)

AE = adverse event; BMI = body mass index; CG = clinical genotyping; CRU = clinical research unit; [REDACTED]; C-SSRS = Columbia-Suicide Severity Rating Scale; D = Day; ECG = electrocardiogram; FSH = follicle-stimulating hormone; IV = intravenous; PK = pharmacokinetic.

- a Subjects will be admitted to the CRU on Day -1 and will be allowed to leave when all assessments on Day 10 have been completed. Subjects will return in the afternoon of Day 14 of Period 1 (which is also Day -1 of Period 2) and will be allowed to leave when all assessments on Day 19 have been completed.
- b The IV infusion of the microdose will start 1.25 hours after the oral study drug administration on Day 1 of Period 1 and Day 14 of Period 2.
- c On Day 1 of Period 1, and Days 7 and 14 of Period 2, subjects are fasted for at least 10 hours prior to dosing. Water will be allowed ad libitum until 1 hour prior to dosing and from 1 hour after dosing. No food is allowed for at least 4 hours postdose. Standardized lunch and dinner are provided 4 and 10 hours postdose, respectively, on Day 1 of Period 1, and Days 7 and 14 of Period 2. Standardized afternoon and evening snacks will be provided as well on these days.
On the other dosing days in the multiple dosing period, subjects will be dosed at least 30 minutes prior to breakfast. On these dosing days, meals will not be standardized.
- d All PK sampling times are relative to oral dosing (see also [Appendix 2](#)).
[REDACTED]
- f Includes measurement of height and BMI.
- g Triplicate ECGs will be collected at screening and Day -1 of Period 1 only. At all other time points a single ECG will be collected (Period 1: Day 10; Period 2: Day -1 of Period 2; predose on Days 6 and 11; Day 18 (96 hours after last dosing); follow-up).
- h Vital signs will be measured at screening (in triplicate), and in Period 1: on Day -1 (in triplicate), Day 1 at 3 hours postdose, Day 2, Day 5; in Period 2: on Day -1, predose on Days 1, 7 and 14; on Day 18 (96 hours after last dosing); follow-up. At screening and on Day -1 of Period 1, vital signs will be measured in triplicate; at other time-points, vital signs will be single measurements.
- i For females only: FSH and serum pregnancy test at screening, and serum pregnancy test only at all other time points.
- j Hematology samples will be collected at screening, Day -1 of Period 1, Day -1 of Period 2; predose on Days 6 and 11 of Period 2; Day 18; follow-up.

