### 17.1.4 Vital Signs

All vital signs data including derived changes from baseline will be listed. For timepoints with triplicate measurements the mean of the triplicate measurements and the change from baseline of the mean triplicate measurements will be listed by subject additionally.

Descriptive statistics will be provided to summarize vital signs including changes from baseline by treatment and scheduled time.

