  - d All PK sampling times are relative to oral dosing (see also [Appendix 3](#)).  
[REDACTED]
  - f Includes measurement of height and BMI.
  - g Triplicate ECGs will be collected at screening and Day -1 of Period 1 only. At all other time points a single ECG will be collected (Period 1: Day 10; Period 2: Day -1 of Period 2; predose on Days 6 and 11; Day 18 (96 hours after last dosing); follow-up).
  - h Vital signs will be measured at screening (in triplicate), and in Period 1: on Day -1 (in triplicate), Day 1 at 3 hours postdose, Day 2, Day 5; in Period 2: on Day -1, predose on Days 1, 7 and 14; on Day 18 (96 hours after last dosing); follow-up. At screening and on Day -1 of Period 1, vital signs will be measured in triplicate; at other time-points, vital signs will be single measurements.
  - i For females only: FSH and serum pregnancy test at screening, and serum pregnancy test only at all other time points.
  - j Hematology samples will be collected at screening, Day -1 of Period 1, Day -1 of Period 2; predose on Days 6 and 11 of Period 2; Day 18; follow-up.
  - k Biochemistry samples will be collected at screening, Day -1 of Period 1, Day -1 of Period 2; predose on Day 11 of Period 2; Day 18; follow-up.  
[REDACTED]

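### Read literally, SAP 9.2.1 bases vital-sign changes on one pre-dose reading although a Day -1 triplicate is collected, and 17.1.4 does not say that the mean is the baseline

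*SAP*

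**What the plan says.** SAP 9.2.1 gives a default that applies unless something else is stated: "baseline for post-dose evaluations within each period is defined as the last observation recorded before the first study drug administration in Period 1". It adds: "The last observation can be an unscheduled / repeated measurement". One exception follows: "Baseline for Electrocardiograms (ECGs) is derived as the mean of the triplicate pre-dose measurements of pre-dose assessments taken in Analysis Period 1". Vital signs are not named there.

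Footnote h of the SAP's schedule of assessments (Appendix 2) sets the replicates: "At screening and on Day -1 of Period 1, vital signs will be measured in triplicate; at other time-points, vital signs will be single measurements". The same footnote in Protocol Appendix 1 gives the Period 1 times: "in Period 1: on Day -1 (in triplicate), Day 1 at 3 hours postdose, Day 2, Day 5". No vital-sign reading is scheduled on Day 1 before dosing.

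SAP 9.2.3 defines a change as the post-dose value minus the baseline value. For vital signs, SAP 17.1.4 says: "For timepoints with triplicate measurements the mean of the triplicate measurements and the change from baseline of the mean triplicate measurements will be listed". This is done for each subject, in addition to the other listings. Its summary sentence promises descriptive statistics of vital signs and their changes without mentioning means. The matching sentence for ECGs in 17.1.5 does refer to mean parameters.

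**The concern.** The default rule takes one observation. Applied as written to vital signs, it uses the last of three Day -1 readings and drops the other two, or lets a later unscheduled repeat displace all three. The better baseline is already being collected.

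One Period 1 baseline serves both periods. An error in it therefore shifts all nine later scheduled assessments of that subject in the same direction: Period 1 Day 1 at 3 hours, Day 2 and Day 5; Period 2 Days -1, 1, 7, 14 and 18; and follow-up. It does not average out over a subject's visits, and each cohort has only 8 subjects.

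The literal rule also departs from the plan's own practice. ECG baseline is averaged, and exclusion criterion 15 in Protocol 4.1.2 judges blood pressure on an average of three or more readings. The documents give no reason to treat the vital-sign baseline differently.

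**Working it through.** **Which value is the baseline?**

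1. Default rule (SAP 9.2.1): the last observation before first dose. ECGs are the only exception there.
2. Last scheduled vital signs before first dose (footnote h): the Day -1 triplicate. The next scheduled reading is 3 hours after dosing.
3. Steps 1 and 2 together give the third Day -1 replicate, or a later unscheduled reading if there is one. SAP 9.1.5 confirms that an unscheduled value may serve as baseline.
4. SAP 17.1.4 treats the triplicate mean as something to list, along with its change from baseline. It does not equate the mean with the baseline.
5. Nothing else settles it. SAP 9.5 says that no table shells will be provided. The datasets marked for double programming in 9.2.4.1 are ADSL, ADPC and ADPP, so ADVS is not among them.

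**How much would the choice matter?**

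The documents give no figure for vital-sign variability, so there is no plan figure to reproduce. Two quantities are assumed:

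- s, the within-subject SD of one reading;
- ρ, the share of within-subject variance common to the three readings of one session (the between-session share).

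The later reading is single and in a different session, and session effects are taken as independent.

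- Single-reading baseline: Var(change) = s² + s² = 2s².
- Mean-of-three baseline: Var(change) = s² + s²[ρ + (1 − ρ)/3].
- SD ratio, mean to single: √{[1 + ρ + (1 − ρ)/3]/2} = √[(2 + ρ)/3].

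| ρ | Variance ratio | SD ratio | Reduction in SD |
|---|---|---|---|
| 0 | 0.667 | 0.816 | 18.4% |
| 0.25 | 0.750 | 0.866 | 13.4% |
| 0.50 | 0.833 | 0.913 | 8.7% |
| 0.75 | 0.917 | 0.957 | 4.3% |
| 0.90 | 0.967 | 0.983 | 1.7% |

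For scale, take n = 8 and an assumed s of 5 or 8 mmHg. The standard error of a cohort mean change with a single-reading baseline is √(2s²/8) = s/2, that is 2.50 or 4.00 mmHg. With the triplicate mean it becomes:

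| Assumed s | ρ = 0 | ρ = 0.5 | ρ = 0.9 |
|---|---|---|---|
| 5 mmHg | 2.04 | 2.28 | 2.46 |
| 8 mmHg | 3.27 | 3.65 | 3.93 |

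This model assumes that every subject has the same true change. If true changes also differ between subjects, that variance is added under both baselines and the relative gain shrinks. For example, with a between-subject variance of true change equal to s² and ρ = 0, the SD ratio is √[(4/3 + 1)/(2 + 1)] = √0.778 = 0.882, a 12% reduction instead of 18%.

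**The case against.** The strongest reply is that the SAP never says the vital-sign baseline is a single reading. The rule in 9.2.1 yields to anything stated elsewhere, and it does not define whether an observation at a triplicate time point is one replicate or the time-point value. The only scheduled vital-sign triplicates are before dosing, so deriving their mean has little use unless it serves as, or is compared with, the baseline. SAP 17.1.5 uses near-identical listing language for ECGs, where the baseline is the triplicate mean.

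This stands in part. A reader might infer from 9.2.1 that the SAP has chosen the last single reading and that every vital-sign change therefore carries avoidable noise. The documents do not support that as a certainty, because 17.1.4 leaves room for the mean. Nor does 17.1.4 settle the matter the other way. Its means are additional listings. If the Day -1 mean were the baseline, its own listed change would be zero for every subject without a later repeat. Its summary sentence also lacks the reference to means found in 17.1.5.

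Two further replies stand. First, 18% is a ceiling: it needs zero between-session variance, yet every later reading is taken on a different day from the baseline. Second, no stated decision depends on the choice. SAP 9.4.3 plans no formal hypothesis testing. The SAP sets category limits for CPK and QTcF but none for vital signs. Protocol 5.3.5.6 makes a vital-sign finding an adverse event through symptoms, a treatment change, an intervention or the investigator's judgement, and not through a computed change.

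**Conclusion.** The point holds as a conditional one. Read literally, 9.2.1 gives vital signs a single-reading baseline, and 17.1.4 does not replace it, so the changes in Table 14.3.4.1 may be noisier than the collected data require. If the literal rule is programmed, moving to the Day -1 mean lowers the SD of within-subject change by between about 2% (ρ = 0.9) and 18% (ρ = 0), with 9% at ρ = 0.5 and 4% at ρ = 0.75. If the mean is already intended, the numbers do not change and only the wording needs repair.

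The sizes rest on assumed variance splits, independent session effects and a common true change; the documents supply none of these. It would be wrong to read 18% as the expected gain, or to infer that a safety conclusion or the bioavailability result is at risk. The effect is confined to descriptive secondary safety summaries, and this is a low-priority improvement.

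**What to change.** Add to SAP 9.2.1: *Baseline for vital signs is the mean of the triplicate measurements on Day -1 of Period 1.* In the same place, state how a later unscheduled pre-dose repeat is handled, for example that it is used only if the triplicate is missing or invalid. Without this, the existing allowance for repeats could still let one reading displace three.

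Leave the ECG rule as it is. State in 17.1.4 that its change-from-baseline listings use this baseline, and use the same baseline in Table 14.3.4.1.

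The cost is two sentences in 9.2.1, a matching phrase in 17.1.4 and the corresponding derivation in ADVS. No new data are needed.
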